10.5. Appendix 5: Genetics

Sample collection information is found in Section [10.1.12](#), Appendix 1.

Use/Analysis of DNA

Genetic variation may impact a participant's response to study intervention, susceptibility to, and severity and progression of disease. Variable response to study intervention may be due to genetic determinants that impact drug absorption, distribution, metabolism, and excretion; mechanism of action of the drug; disease etiology; and/or molecular subtype of the disease being treated. Therefore, where local regulations and IRB/IEC allow, a blood sample will be collected for DNA analysis from consenting participants.

DNA samples may be used for research related to SARS-CoV-2 and related diseases. They may also be used to develop tests/assays including diagnostic tests related to LY3819253, LY3832479, or SARS-CoV-2. Genetic research may consist of the analysis of one or more candidate genes or the analysis of genetic markers throughout the genome as appropriate.

The samples may be analyzed as part of a multi-study assessment of genetic factors involved in the response to LY3819253, LY3832479, or study interventions of this class to understand study disease or related conditions.

The results of genetic analyses may be reported in the CSR or in a separate study summary.

The sponsor will store the DNA samples in a secure storage space with adequate measures to protect confidentiality.

The samples will be retained at a facility selected by the sponsor or its designee while research on SARS-CoV-2 continues but no longer than 7 years or other period as per local requirements.

10.6. Appendix 6: Recommended Laboratory Testing for Hypersensitivity Events

Laboratory assessments should be performed if the participant experiences generalized urticaria or if anaphylaxis is suspected.

- Collect sample after the participant has been stabilized, and within 1 to 2 hours of the event; however, samples may be obtained as late as 12 hours after the event as analytes can remain altered for an extended period of time. Record the time at which the sample was collected.
- Obtain a follow-up sample at the next regularly scheduled visit or after approximately 4 weeks, whichever is later.

Clinical Lab Tests for Hypersensitivity Events

Hypersensitivity Tests	Notes
	Selected test may be obtained in the event of anaphylaxis or systemic allergic/hypersensitivity reactions.
LY3819253 and LY3832479 antidrug antibodies (immunogenicity/ADA)	Assayed by Lilly-designated laboratory. Results will not be provided to the investigative sites.
LY3819253 and LY3832479 concentrations (PK)	Assayed by Lilly-designated laboratory. Results will not be provided to the investigative sites.
Tryptase	Assayed by Lilly-designated laboratory. Results will not be provided to the investigative sites. Urine N-methylhistamine testing is performed in addition to tryptase testing. Collect the first void urine following the event. Collect a follow-up urine sample after approximately 4 weeks. Note: If a tryptase sample is obtained more than 2 hours after the event (that is, within 2 to 12 hours), or is not obtained because more than 12 hours have lapsed since the event, collect a urine sample for N-methylhistamine testing.
N-methylhistamine	Assayed by Lilly-designated laboratory. Results will not be provided to the investigative sites.
Drug-specific IgE	Will be performed if a validated assay is available. Assayed by Lilly-designated laboratory. Results will not be provided to the investigative sites.
Basophil activation test	Will be performed if a validated assay is available. Assayed by Lilly-designated laboratory. Results will not be provided to the investigative sites. NOTE: The basophil activation test is an in vitro cell based assay that only requires a serum sample. It is a surrogate assay for drug specific IgE but is not specific for IgE.
Complement (C3, C3a and C5a)	Assayed by Lilly-designated laboratory. Results will not be provided to the investigative sites.
Cytokine panel	Assayed by Lilly-designated laboratory. Results will not be provided to the investigative sites.

Abbreviations: ADA = antidrug antibody; IgE = immunoglobulin E; PK = pharmacokinetic.

10.7. Appendix 7: Liver Safety: Suggested Actions and Follow-up Assessments

Close Hepatic Monitoring

This table describes when close hepatic monitoring should occur.

If a participant with baseline results of ...	develops the following elevations...
ALT or AST $<1.5 \times$ ULN	ALT or AST $\geq 3 \times$ ULN
ALP $<1.5 \times$ ULN	ALP $\geq 2 \times$ ULN
TBL $<1.5 \times$ ULN	TBL $\geq 2 \times$ ULN (except for participants with Gilbert's syndrome)
ALT or AST $\geq 1.5 \times$ ULN	ALT or AST $\geq 2 \times$ baseline
ALP $\geq 1.5 \times$ ULN	ALP $\geq 2 \times$ baseline
TBL $\geq 1.5 \times$ ULN	TBL $\geq 2 \times$ baseline (except for participants with Gilbert's syndrome)

Abbreviations: ALP = alkaline phosphatase; ALT = alanine aminotransferase; AST = aspartate aminotransferase; TBL = total bilirubin; ULN = upper limit of normal.

The laboratory tests listed in Section 10.2, Appendix 2, including alanine aminotransferase (ALT), AST, ALP, total bilirubin (TBL), direct bilirubin, gamma-glutamyl transferase, and creatine kinase, should be repeated when monitoring labs are performed.

If the abnormality persists or worsens, clinical and laboratory monitoring, and evaluation for the possible causes of the abnormal liver tests should be initiated by the investigator in consultation with the sponsor.

At a minimum, this evaluation should include a physical examination and a thorough medical history, including symptoms, recent illnesses (for example, heart failure, systemic infection, hypotension, seizures) recent travel, history of concomitant medications (including over-the-counter), herbal and dietary supplements, history of alcohol use, and other substance abuse.

Initially, monitoring of symptoms and hepatic biochemical tests should be done at a frequency of between 3 times weekly and every other week, based on the participant's clinical condition and hepatic biochemical tests. Subsequently, the frequency of monitoring may be lowered to once every 1 to 2 weeks if the participant's clinical condition and laboratory results stabilize.

Monitoring of ALT, AST, ALP, and TBL should continue until levels normalize or return to approximate baseline levels.

Comprehensive Hepatic Evaluation

A comprehensive evaluation should be performed to search for possible causes of liver injury if one or more of these conditions occur:

If a participant with baseline results of...	develops the following elevations...
ALT or AST $<1.5 \times$ ULN	ALT or AST $\geq 3 \times$ ULN with hepatic signs/symptoms*, or ALT or AST $\geq 5 \times$ ULN
ALP $<1.5 \times$ ULN	ALP $\geq 3 \times$ ULN
TBL $<1.5 \times$ ULN	TBL $\geq 2 \times$ ULN (except for participants with Gilbert's syndrome)
ALT or AST $\geq 1.5 \times$ ULN	ALT or AST $\geq 2 \times$ baseline with hepatic signs/symptoms*, or ALT or AST $\geq 3 \times$ baseline
ALP $\geq 1.5 \times$ ULN	ALP $\geq 2 \times$ baseline
TBL $\geq 1.5 \times$ ULN	TBL $\geq 1.5 \times$ baseline (except for participants with Gilbert's syndrome)

* Hepatic signs/symptoms are severe fatigue, nausea, vomiting, right upper quadrant abdominal pain, fever, rash, and/or eosinophilia $>5\%$.

Abbreviations: ALP = alkaline phosphatase; ALT = alanine aminotransferase; AST = aspartate aminotransferase; TBL = total bilirubin; ULN = upper limit of normal.

At a minimum, this evaluation should include physical examination and a thorough medical history, as outlined above, as well as tests for PT-INR; tests for viral hepatitis A, B, C, or E; tests for autoimmune hepatitis; and an abdominal imaging study (for example, ultrasound or CT scan).

Based on the participant's history and initial results, further testing should be considered in consultation with the Lilly-designated medical monitor, including tests for hepatitis D virus (HDV), cytomegalovirus (CMV), Epstein-Barr virus (EBV), acetaminophen levels, acetaminophen protein adducts, urine toxicology screen, Wilson's disease, blood alcohol levels, urinary ethyl glucuronide, and serum phosphatidylethanol.

Based on the circumstances and the investigator's assessment of the participant's clinical condition, the investigator should consider referring the participant for a hepatologist or gastroenterologist consultation, magnetic resonance cholangiopancreatography (MRCP), endoscopic retrograde cholangiopancreatography (ERCP), cardiac echocardiogram, or a liver biopsy.

Additional Hepatic Data Collection (Hepatic Safety CRF)

Additional hepatic safety data collection in hepatic safety CRFs should be performed in study participants who either have a hepatic event considered to be an SAE or meet 1 or more of these conditions:

If a participant with baseline...	has the following elevations...
ALT <1.5 × ULN	ALT ≥5 × ULN on 2 or more consecutive blood tests
ALP <1.5 × ULN	ALP ≥2 × ULN on 2 or more consecutive blood tests
TBL <1.5 × ULN	TBL ≥2 × ULN, except for cases of known Gilbert's syndrome
ALT ≥1.5 × ULN	ALT ≥3 × baseline on 2 or more consecutive blood tests
ALP ≥1.5 × ULN	ALP ≥2 × baseline on 2 or more consecutive blood tests
TBL ≥1.5 × ULN	TBL ≥2 × baseline

Abbreviations: ALP = alkaline phosphatase; ALT = alanine aminotransferase; AST = aspartate aminotransferase; TBL = total bilirubin; ULN = upper limit of normal.

Note: The interval between the 2 consecutive blood tests should be at least 2 days.

Hepatic Evaluation Testing

The Lilly-designated central laboratory must complete the analysis of all selected testing except for microbiology testing.

Local testing may be performed in addition to central testing when necessary for immediate participant management.

Results will be reported if a validated test or calculation is available.

Hematology	Clinical Chemistry
Hemoglobin	Total bilirubin
Hematocrit	Direct bilirubin
Erythrocytes (RBCs - red blood cells)	Alkaline phosphatase (ALP)
Leukocytes (WBCs - white blood cells)	Alanine aminotransferase (ALT)
Differential:	Aspartate aminotransferase (AST)
Neutrophils, segmented	Gamma-glutamyl transferase (GGT)
Lymphocytes	Creatine kinase (CK)
Monocytes	Other Chemistry
Basophils	Acetaminophen
Eosinophils	Acetaminophen protein adducts
Platelets	Alkaline phosphatase isoenzymes
Cell morphology (RBC and WBC)	Ceruloplasmin
Coagulation	Copper
	Ethyl alcohol (EtOH)
Prothrombin time, INR (PT-INR)	Haptoglobin
Serology	Immunoglobulin IgA (quantitative)

Hepatitis A virus (HAV) testing:	Immunoglobulin IgG (quantitative)
HAV total antibody	Immunoglobulin IgM (quantitative)
HAV IgM antibody	Phosphatidylethanol (PEth)
Hepatitis B virus (HBV) testing:	Urine Chemistry
Hepatitis B surface antigen (HBsAg)	Drug screen
Hepatitis B surface antibody (anti-HBs)	Ethyl glucuronide (EtG)
Hepatitis B core total antibody (anti-HBc)	Other Serology
Hepatitis B core IgM antibody	Anti-nuclear antibody (ANA)
Hepatitis B core IgG antibody	Anti-smooth muscle antibody (ASMA) ^a
HBV DNA ^b	Anti-actin antibody ^c
Hepatitis C virus (HCV) testing:	Epstein-Barr virus (EBV) testing:
HCV antibody	EBV antibody
HCV RNA ^b	EBV DNA ^b
Hepatitis D virus (HDV) testing:	Cytomegalovirus (CMV) testing:
HDV antibody	CMV antibody
Hepatitis E virus (HEV) testing:	CMV DNA ^b
HEV IgG antibody	Herpes simplex virus (HSV) testing:
HEV IgM antibody	HSV (Type 1 and 2) antibody
HEV RNA ^b	HSV (Type 1 and 2) DNA ^b
Microbiology ^d	Liver kidney microsomal type 1 (LKM-1) antibody
Culture:	
Blood	
Urine	

^a Not required if anti-actin antibody is tested.

^b Reflex/confirmation dependent on regulatory requirements, testing availability, or both.

^c Not required if anti-smooth muscle antibody (ASMA) is tested.

^d Assayed ONLY by investigator-designated local laboratory; no central testing available.

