Clinical status and concomitant procedures of special interest in hospitalized participants		Daily		X	X		Documentation from hospital records is acceptable. Includes: consciousness status (ACVPU), limitation on activities due to COVID-19, and requirements for 
Ongoing hospital medical careSupplemental oxygennon-invasive ventilation or a high flow oxygen devicemechanical ventilationextracorporeal membrane oxygenation, oradditional organ support (e.g. pressors, renal replacement)
SARS-CoV-2 Serology		X		X	X	X	Day 1: pre-dose. assessed at a central laboratory
Documentation of positive SARS-CoV-2 viral infection	X						Applies to participants in Part 3 only. Sample for first positive test must be collected within 10 days prior to start of infusion. Local laboratory and/or Point-of-Care testing.

Procedures	Screening	Evaluation Period			ETV	Post-treatment follow-up	Comments
Study Day	Max 7 day window	1	8	29		85	
Visit window (\pm number of days)	--	--	1	2		7	
SARS-CoV-2 nasopharyngeal swab taken from both nostrils		X	X	X	X	X	Day 1: pre-dose. assessed at a central laboratory No samples needed if participant is hospitalized.*
Urine pregnancy	X	X			X	X	Only for WOCBP (Section 10.4, Appendix 4) Local laboratory. Test performed in the 24 hours prior to study entry will be accepted for determination of eligibility. No samples needed if participant is hospitalized.*
Hematology		X		X	X	X	Day 1: pre-dose. Assayed by Lilly-designated laboratory No samples needed if participant is hospitalized.*
Clinical Chemistry		X		X	X	X	Day 1: pre-dose. Assayed by Lilly-designated laboratory No samples needed if participant is hospitalized.*

 • C-reactive protein; high-sensitivity • Ferritin • D-dimer • Procalcitonin • Troponin 		X		X	X		Day 1: pre-dose. Assayed by Lilly-designated laboratory No samples needed if participant is hospitalized.*
PK sample		X		X	X	X	Day 1: post-dose only (approx. 30 minutes after end of infusion) Assayed by Lilly-designated laboratory No samples needed if participant is hospitalized.*
Immunogenicity (ADA) sample		X		X	X	X	Day 1: pre-dose. Remaining days: Collect with time-matched PK sample. No samples needed if participant is hospitalized.*

Procedures	Screening	Evaluation Period			ETV	Post-treatment follow-up	Comments
Study Day	Max 7 day window	1	8	29		85	
Visit window (± number of days)	--	--	1	2		7	

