8.2.3. Clinical Safety Laboratory Assessments

See Section 10.2, Appendix 2 for the list of clinical laboratory tests to be performed and the SoA for the timing and frequency. All protocol-required laboratory assessments, as defined in Appendix 2, must be conducted in accordance with the laboratory manual and the SoA.

Clinically significant abnormal laboratory findings are those which are not associated with the underlying disease, unless judged by the investigator to be more severe than expected for the participant's condition.

All laboratory tests with values considered clinically significantly abnormal during participation in the study or within 28 days after the dose of study intervention should be repeated until the values return to normal or baseline or are no longer considered clinically significant by the investigator or sponsor.

If such values do not return to normal/baseline within a period of time judged reasonable by the investigator, the etiology should be identified and the sponsor notified.

The investigator must review the laboratory results, document this review, and record any clinically relevant changes occurring during the study in the CRF.

The laboratory reports must be filed with the source documents.

If laboratory values from non-protocol specified laboratory assessments performed at a local laboratory that require a change in participant management or are considered clinically significant by the investigator (i.e., SAE or AE), then the AE or SAE will be recorded by the investigator in the CRF.

Pregnancy Testing

Women of childbearing potential (WOCBP) must undergo pregnancy testing according to the SoA.

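### For raised baseline bilirubin, Appendix 7 starts the full hepatic work-up at 1.5 x baseline but close monitoring only at 2 x baseline, the one inverted row of six

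*Protocol*

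**What the plan says.** Protocol Section 10.7 (Appendix 7) sets triggers in separate tables for close hepatic monitoring, comprehensive hepatic evaluation and completion of the hepatic safety CRF. Each table splits participants by whether the baseline value is below, or at least, 1.5 x ULN.

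For baseline TBL of at least 1.5 x ULN:

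- Close monitoring is triggered at "TBL $\geq 2 \times$ baseline".
- Comprehensive evaluation is triggered at "TBL $\geq 1.5 \times$ baseline".
- Both cells carry the same exception for Gilbert's syndrome.
- The hepatic safety CRF trigger is 2 x baseline.

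The instructions on serial testing stand only under Close Hepatic Monitoring. At first, "monitoring of symptoms and hepatic biochemical tests should be done at a frequency of between 3 times weekly and every other week"; the interval may later be relaxed to every one to two weeks. Monitoring of ALT, AST, ALP and TBL "should continue until levels normalize or return to approximate baseline levels". This monitoring is conditional: "If the abnormality persists or worsens, clinical and laboratory monitoring, and evaluation for the possible causes" are to be initiated.

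The comprehensive evaluation repeats the physical examination and history, and adds PT-INR, viral and autoimmune hepatitis tests and abdominal imaging. It states no repeat interval and no stopping rule.

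**The concern.** A tiered safety scheme should begin the lighter step no later than the heavier one. Here a bilirubin of 1.5 to <2 x a raised baseline satisfies the criterion for the work-up but not the criterion for monitoring. Followed to the letter, the site looks for a cause but has no stated interval for rechecking bilirubin and no statement of when rechecking may end.

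What is at stake is consistent safety follow-up in a small group. Sites hold two thresholds in the wrong order for the same analyte and stratum, and the documents do not show which value was intended. Participants with raised baseline bilirubin can enrol: no exclusion criterion in Section 5.2 names bilirubin or liver disease, and criterion 18 leaves serious concomitant disease to the investigator's judgement.

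**Working it through.** **Step 1: compare the two tables row by row** (Section 10.7, Close Hepatic Monitoring and Comprehensive Hepatic Evaluation).

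| Baseline | Close monitoring | Comprehensive evaluation | Order |
|---|---|---|---|
| ALT/AST <1.5 x ULN | 3 x ULN | 3 x ULN with signs or symptoms, or 5 x ULN | ordered |
| ALP <1.5 x ULN | 2 x ULN | 3 x ULN | ordered |
| TBL <1.5 x ULN | 2 x ULN | 2 x ULN | equal |
| ALT/AST >=1.5 x ULN | 2 x baseline | 2 x baseline with signs or symptoms, or 3 x baseline | ordered |
| ALP >=1.5 x ULN | 2 x baseline | 2 x baseline | equal |
| TBL >=1.5 x ULN | 2 x baseline | 1.5 x baseline | **inverted** |

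Three rows are ordered, two are equal and one is inverted. The Gilbert's exception is identical in the two TBL cells, so it does not explain the difference.

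**Step 2: width of the affected window.** Lower limit = 1.5 x baseline; upper limit = 2 x baseline.

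- Baseline 1.5 x ULN: 1.5 x 1.5 = 2.25 to <2 x 1.5 = 3.0 x ULN.
- Baseline 2 x ULN: 1.5 x 2 = 3.0 to <2 x 2 = 4.0 x ULN.

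**Step 3: what the visit schedule alone supplies.** In the Part 2 Treatment Cohort and Part 3 (Section 1.3.2), clinical chemistry is drawn on Day 1, Day 29, at early termination and on Day 85. The visit windows are 2 days at Day 29 and 7 days at Day 85. For a rise found at Day 29:

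- Nominal time to the next scheduled chemistry: 85 - 29 = 56 days.
- Shortest: (85 - 7) - (29 + 2) = 78 - 31 = 47 days.
- Longest: (85 + 7) - (29 - 2) = 92 - 27 = 65 days.

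The longest interval suggested under close monitoring is every other week, or 14 days, if the abnormality persists. The 56 days is the spacing of scheduled draws. It is not the expected gap in testing, because an investigator doing the work-up may well repeat bilirubin sooner.

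For Part 1 and the Part 2 Prevention Cohort the chemistry row has six marks, but the columns may be displaced in the text available, so no gap is calculated.

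**Step 4: how many participants follow that schedule** (Section 9.2, approximate planned numbers).

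- Part 2 Treatment Cohort: 2000 - 1700 = about 300.
- Part 3: up to about 500, and possibly as few as 30.
- Together: at most about 300 + 500 = 800.
- Planned total over the three parts: 1700 + 2000 + 500 = 4200, so 800/4200 = 19%. Against the stated study maximum of about 5000 it is 800/5000 = 16%.

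These shares describe schedule coverage only. The affected group is the far narrower set with baseline TBL of at least 1.5 x ULN, no Gilbert's syndrome and a later value inside the window. The documents give no count for it.

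**The case against.** The strongest reply is that the inversion errs towards more action. A participant in the window receives the stronger step, and the hepatic test list in Appendix 7 includes total and direct bilirubin, ALT, AST and ALP. That stands: no work-up is missed.

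Second, Section 8.2.3 already says that clinically significant abnormal laboratory values "should be repeated until the values return to normal or baseline or are no longer considered clinically significant by the investigator or sponsor", and Appendix 2 (Section 10.2) allows extra tests whenever the investigator finds them necessary. This largely replaces the missing stopping rule, but not entirely. Section 8.2.3 sets no interval, and it depends on a judgement of clinical significance that leaves out findings associated with the underlying disease unless they are more severe than expected.

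Third, the appendix is headed as suggested actions, and the monitoring it describes begins only when an abnormality continues or worsens. That is correct, and it is why the point is minor.

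Fourth, the hepatic safety CRF trigger for this stratum is also 2 x baseline, so 1.5 x baseline is the odd value of three. This bears on what may have been intended but does not settle it. The CRF table governs data collection, and a CRF threshold above the clinical triggers is not out of order.

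**Conclusion.** The threshold is wrong as written: within one stratum the lighter step is triggered later than the heavier one, and no other row does this. The effect is confined to non-Gilbert's participants with baseline bilirubin of at least 1.5 x ULN whose value rises to 1.5 to <2 x baseline. What they lack is the suggested repeat interval and an explicit rule to continue until recovery. They do not lack the work-up itself. No efficacy result is affected.

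This rests on reading the tables literally, and on the assumption, which the documents do not allow to be checked, that few participants have such a baseline. The inconsistency itself is certain. Correcting it is optional.

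**What to change.** In the Close Hepatic Monitoring table, change the trigger for baseline TBL of at least 1.5 x ULN from 2 x baseline to 1.5 x baseline, and keep the Gilbert's syndrome exception. The row would then be equal across the two tiers, as two other rows already are.

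Leave the comprehensive-evaluation trigger at 1.5 x baseline. Raising it would also restore the order, but by reducing protection. The sponsor should confirm the intended value when making the change. The CRF trigger can stay at 2 x baseline.

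The cost is one table cell at the next amendment and a few extra blood draws in what is probably a small number of participants.

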10.8. Appendix 8: Abbreviations

Term	Definition
ADA	antidrug antibody
ADE	antibody-dependent enhancement
AE	adverse event
ALT	alanine aminotransferase
ANOVA	analysis of variance
AST	aspartate aminotransferase
blinding/masking	
A single-blind study is one in which the investigator and/or his staff are aware of the treatment but the participant is not, or vice versa, or when the sponsor is aware of the treatment but the investigator and/his staff and the participant are not.
 
A double-blind study is one in which neither the participant nor any of the investigator or sponsor staff who are involved in the treatment or clinical evaluation of the subjects are aware of the treatment received.

Companion diagnostic	An in vitro diagnostic device (assay or test) that provides information that is essential for the safe and effective use of a corresponding therapeutic product
complaint	A complaint is any written, electronic, or oral communication that alleges deficiencies related to the identity, quality, purity, durability, reliability, safety or effectiveness, or performance of a drug or drug delivery system.
compliance	Adherence to all study-related, good clinical practice (GCP), and applicable regulatory requirements.
COVID-19	Coronavirus disease - 2019
CRF	Case report form
CRP	clinical research physician: Individual responsible for the medical conduct of the study. Responsibilities of the CRP may be performed by a physician, clinical research scientist, global safety physician or other medical officer.
CRS	Clinical research scientist
CSR	clinical study report
CTA	Clinical trial agreement
DAIDS	Division of AIDS
DMC	Data monitoring committee; functionally equivalent to DSMB for this study
DSMB	Data safety monitoring board
Device Deficiencies	Equivalent to product complaint

EDC	Electronic data capture
enroll	The act of assigning a participant to a treatment. Participants who are enrolled in the study are those who have been assigned to a treatment.
enter	Participants entered into a study are those who sign the informed consent form directly or through their legally acceptable representatives.
Facility	The physical location for the conduct of study procedures. This will be the skilled nursing and assisted living facilities associated with the nursing home network. See also "Skilled nursing and Assisted Living facility".
Facility staff	Participants who are staff of the facility. For "facility", see "Facility" and "Skilled nursing and Assisted Living facility". Contrast to "Site staff"
GCP	good clinical practice
IB	Investigator's Brochure
ICF	informed consent form
IgG1	immunoglobulin G1
Informed consent	A process by which a participant voluntarily confirms his or her willingness to participate in a particular study, after having been informed of all aspects of the study that are relevant to the participant's decision to participate. Informed consent is documented by means of a written, signed and dated informed consent form.
interim analysis	An interim analysis is an analysis of clinical study data, separated into treatment groups, that is conducted before the final reporting database is created/locked.
IP	investigational product
IRB/IEC	Institutional review board / independent ethics committee
ITT	intent to treat: The principle that asserts that the effect of a treatment policy can be best assessed by evaluating on the basis of the intention to treat a participant (that is, the planned treatment regimen) rather than the actual treatment given. It has the consequence that participant allocated to a treatment group should be followed up, assessed, and analyzed as members of that group irrespective of their compliance to the planned course of treatment.
IV	intravenous
IWRS	interactive web-response system
LS mean	least-squares mean
mAb	monoclonal antibody
MMRM	mixed-effects model for repeated measures

NIAID	National Institute of Allergy and Infectious Diseases
participant	Equivalent to CDISC term “subject”: an individual who participates in a clinical trial, either as recipient of an investigational medicinal product or as a control
PK/PD	pharmacokinetics/pharmacodynamics
POC	Point of care test. In this study, the POC test is a rapid POC test that returns results in minutes.
Prevention Cohort	Participants in Part 2 who test negative during screening on the POC test. Contrast with “Treatment Cohort”.
RT-PCR	reverse transcription – polymerase chain reaction
SAE	serious adverse event
SAP	statistical analysis plan
SARS	severe acute respiratory syndrome
SARS-CoV-2	severe acute respiratory syndrome coronavirus 2
screen	The act of determining if an individual meets minimum requirements to become part of a pool of potential candidates for participation in a clinical study.
Site	The physical location of the primary investigator and associated study staff who will conduct study procedures at the facilities.
Site staff	Site personnel who perform study tasks. Contrast to “Facility staff”
Skilled nursing and Assisted Living facility	This terminology is intended to be broad and is inclusive of skilled nursing, assisted living, long-term care, or nursing home facilities. Memory care units in any of the above can be included. Also, this terminology includes residents who may need only short-term care.
SoA	Schedule of Activities
TBL	total bilirubin
TE-ADA	treatment-emergent antidrug antibody
TE-ADA+	treatment-emergent antidrug antibody positive
TEAE	treatment-emergent adverse event: An untoward medical occurrence that emerges during a defined treatment period, having been absent pretreatment, or worsens relative to the pretreatment state, and does not necessarily have to have a causal relationship with this treatment.
Treatment Cohort	Participants in Part 2 who test positive during screening on the POC test. Contrast with “Prevention Cohort”.
WOCBP	women of childbearing potential

